September 1, 2014

Study Title: Measurement of Cerebral Blood Flow Using Transcranial Doppler Ultrasound in Children with Sickle Cell Disease NCT: NCT02090881 Protocol ID: 13HH0858

Patients with SCD age 2 to 16 years attending our tertiary paediatric haematology clinic for stroke surveillance were eligible. The study was conducted as part of a higher degree in vascular imaging and hence the study duration was limited to six months. Based on patient numbers within the service, we aimed to study 25 consecutive patients referred to the vascular sciences department for routine TCD scanning. Ethical approval was obtained from the local research ethics committee (ref 13/LO/1503) and IRAS ID 133045) and written informed consent was obtained from legal guardians. A pulsatile flow simulating phantom was used to eliminate patient variability. Study participants were scanned by a single operator with imaging TCCD. Initially a full TCD assessment was performed using the non-portable Philips IU-22 with a S5-1 phased array transducer (5.0-1.0MHz). The measurement was then repeated in every patient in only the MCA on each side of the head using the portable Zonare Z-One scanner with a P4-1C phased array transducer (4.0-1.8MHz). For both examinations, a standardised screening protocol was used recording velocities from the transtemporal windows, a 5mm sample volume size, with no angle correction. Gain was adjusted in order to clearly see the spectral Doppler velocity waveform without the presence of noise in the background. For the purpose of this study, the TAMM velocities were compared because stroke risk categorisation according to the STOP trial was based on TAMM velocity, not peak systolic or end diastolic velocities. Each study was categorised as normal, conditional, abnormal or inadequate according to criteria previously developed by the STOP protocol. The participants were not permitted to sleep during the scan to avoid increase in blood carbon dioxide levels in sleep, which can result in increase in TCD velocities. Methods Patients with SCD age 2 to 16 years attending our tertiary paediatric haematology clinic for stroke surveillance were eligible. The study was conducted as part of a higher degree in vascular imaging and hence the study duration was limited to six months. Based on patient numbers within the service, we aimed to study 25 consecutive patients referred to the vascular sciences department for routine TCD scanning. Ethical approval was obtained from the local research ethics committee (ref 13/LO/1503) and IRAS ID 133045) and written informed consent was obtained from legal guardians.

A pulsatile flow simulating phantom was used to eliminate patient variability. Study participants were scanned by a single operator with imaging TCCD. Initially a full TCD assessment was performed using the non-portable Philips IU-22 with a S5-1 phased array transducer (5.0-1.0MHz). The measurement was then repeated in every patient in only the MCA on each side of the head using the portable Zonare Z-One scanner with a P4-1C phased array transducer (4.0-1.8MHz). For both examinations, a standardised screening protocol was used recording velocities from the transtemporal windows, a 5mm sample volume size, with no angle correction. Gain was adjusted in order to clearly see the spectral Doppler velocity waveform without the presence of noise in the background. For the purpose of this study, the TAMM velocities were compared because stroke risk categorisation according to the STOP trial was based on TAMM velocity, not peak systolic or end diastolic velocities. Each study was categorised as normal, conditional, abnormal or inadequate according to criteria previously developed by the STOP protocol. The participants were not permitted to sleep during the scan to avoid increase in blood carbon dioxide levels in sleep, which can result in increase in TCD velocities.

Study Title: Measurement of Cerebral Blood Flow Using Transcranial Doppler Ultrasound in Children with Sickle Cell Disease NCT: NCT02090881 Protocol ID: 13HH0858 Statistical Analysis Spearman's Correlation Coefficients were calculated to assess the relationships between different parameters in

September 1, 2014

order to assess the strength of the association between the two measures. Intra-class Coefficient Correlation (ICC) and 95% confidence intervals were used to provide a measure of the strength of the association between the measurements from both pieces of equipment and therefore the validity of the measurement. It has been stated that $ICC > 0.75$ implies acceptable validity.

BlandAltman plots were used to estimate the agreement between TAMM velocity measurements by determining how much the velocity from one machine differs from another. Statistical analyses were performed using SPSS Statistics version 21 (IBM). The level of statistical significance was defined as $p < 0.05$.

Conclusion The purpose of this pilot study was to evaluate the use of a portable ultrasound machine by comparison with an established laboratory-based ultrasound machine. This study demonstrated complete agreement in stroke risk categorisation between the two instruments. As a pilot study, it confirms the feasibility and clinical significance of this investigation. A larger sample size with a greater range in TAMM velocities is needed to further investigate the correlation between different ultrasound machines at extremes of measurement such as very high or very low velocities. Further evidence is needed in order to establish the implications these differences may have on screening

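### One operator takes both MCA readings in the same child with no masking described, so agreement between the two machines may be overstated by an unknown amount

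*Combined protocol and SAP*

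**What the plan says.** The design facts are in the Methods section, whose text is printed twice in the same form.

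- Operator: "Study participants were scanned by a single operator with imaging TCCD".
- First reading: "Initially a full TCD assessment was performed using the non-portable Philips IU-22".
- Second reading: "The measurement was then repeated in every patient in only the MCA on each side of the head using the portable Zonare Z-One scanner".
- Gain, for both examinations: "Gain was adjusted in order to clearly see the spectral Doppler velocity waveform without the presence of noise in the background".
- Settings held common to both machines: "a standardised screening protocol was used recording velocities from the transtemporal windows, a 5mm sample volume size, with no angle correction".
- Phantom: "A pulsatile flow simulating phantom was used to eliminate patient variability". Its readings and their analysis are not described.

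The Statistical Analysis section compares the paired TAMM velocities by Spearman correlation, by ICC with 95% confidence intervals (above 0.75 taken as acceptable validity) and by Bland-Altman plots. The Conclusion reports: "This study demonstrated complete agreement in stroke risk categorisation between the two instruments".

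The documents do not mention masking of the first result, coded or independent re-reading, or who assigned the STOP categories. They do not say whether TAMM was measured during the scan or afterwards.

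**The concern.** An agreement study needs each machine's reading to be obtained without reference to the other. As described, the person taking every Zonare reading has just examined the same vessel in the same child on the Philips. The second reading leaves that person some discretion: finding the vessel through the window, deciding which waveform to accept and setting the gain. If the first value is in mind, these choices can drift toward reproducing it.

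The direction of such a drift is not neutral. It reduces paired differences, which favours the finding the study reports. A child whose velocity lies near a category boundary is most exposed, because a small shift can decide whether the categories match.

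This is separate from the fixed scan order. Alternating the order would balance a mean shift due to order, but whichever machine came second could still be read with knowledge of the first. The larger sample and wider velocity range that the Conclusion calls for would not remove the problem either. A bigger study run the same way would estimate the same inflated agreement more precisely.

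**Working it through.** **Plan's own figure.** There is none to reproduce. The target of 25 children rests on service numbers and a six-month limit, with no precision target for the ICC or the limits of agreement.

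**Inputs.** From the documents: the ICC benchmark of 0.75, 25 children, two sides and two machines. Assumed, because the documents give neither: the pull k and the true ICC, written ρ.

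**Model.** Let P be the first (Philips) reading and Z the Zonare reading that would have been obtained without knowledge of P. Take equal variances of 1, covariance ρ and no systematic difference between machines. The recorded second reading is Z′ = (1 − k)Z + kP.

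**Step 1: differences.** Z′ − P = (1 − k)(Z − P). The mean difference and the width of the limits of agreement are both multiplied by (1 − k). With k = 0.20 the limits are 20% too narrow; with k = 0.30, 30%.

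**Step 2: ICC.**

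- Cov(P, Z′) = (1 − k)ρ + k
- Var(Z′) = (1 − k)² + k² + 2k(1 − k)ρ
- Apparent ICC = 2 Cov(P, Z′) / [1 + Var(Z′)]

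| k | True ICC | Calculation | Apparent ICC | Above 0.75? |
|---|---|---|---|---|
| 0.10 | 0.65 | 1.37 / 1.937 | 0.71 | No |
| 0.20 | 0.60 | 1.36 / 1.872 | 0.73 | No |
| 0.20 | 0.65 | 1.44 / 1.888 | 0.76 | Yes |
| 0.30 | 0.50 | 1.30 / 1.79 | 0.73 | No |
| 0.30 | 0.60 | 1.44 / 1.832 | 0.79 | Yes |
| 0.30 | 0.75 | 1.65 / 1.895 | 0.87 | Yes |

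**Step 3: lowest true ICC that reaches 0.75.** Set the apparent ICC equal to 0.75 and solve for ρ.

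- k = 0.10: 1.8ρ + 0.2 = 1.365 + 0.135ρ, so ρ = 1.165 / 1.665 = 0.70.
- k = 0.20: 1.6ρ + 0.4 = 1.26 + 0.24ρ, so ρ = 0.86 / 1.36 = 0.63.
- k = 0.30: 1.4ρ + 0.6 = 1.185 + 0.315ρ, so ρ = 0.585 / 1.085 = 0.54.

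**Step 4: categories.** For a single vessel, with k between 0 and 1, Z′ lies between Z and P. On velocity-defined categories the pull therefore cannot create a mismatch where Z and P already agreed, and it can remove one where they did not.

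**Step 5: size of the remedy.** 25 children × 2 sides × 2 machines = 100 spectra, assuming one stored spectrum per side and machine and full recruitment.

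**The case against.** The strongest reply is that the documents are silent on masking; they do not say it was absent. A reader might infer that the operator knew each child's first velocity and category when taking the second reading, and that agreement is therefore overstated. The text does not establish that. It does not say whether TAMM was measured live or later, whether values were on display, or when and by whom categories were assigned. This objection stands, and it limits the point to a risk.

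A second tempting inference is that a 20–30% pull would carry any failing machine past 0.75. It would not: a true 0.60 with k = 0.20 and a true 0.50 with k = 0.30 both give about 0.73. A machine whose true ICC exceeds 0.75 passes without any pull.

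The plan also deserves credit for its safeguards. A single operator removes between-operator variation, and the common window, sample volume and angle rule narrow discretion. Neither makes the second reading independent of the first, because waveform choice and gain remain with the operator. The phantom could offer a check free of patient variation, but it does not mask readings in children and no analysis of it is described.

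Finally, the Conclusion calls the work a pilot, asks for a larger sample and says more evidence is needed on what machine differences mean for screening. That tempers the claim, but it does not mention this source of bias.

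**Conclusion.** The point holds as a risk of bias in a known direction and of unknown size. Followed as written, the procedure leaves the second reading open to being drawn toward the first, and the stated safeguards do not close that gap. If the first value was known, the limits of agreement may be too narrow, the ICC too high and category matches too frequent.

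The figures are illustrative. They rest on a constant proportional pull, equal variances, no systematic machine difference, and assumed values of k and the true ICC. Under those assumptions the 0.75 benchmark is reached only from a true ICC of at least about 0.70, 0.63 or 0.54 for k of 0.10, 0.20 or 0.30; from lower true values it is not. Whether this study's result was affected cannot be determined from the documents. The matter is worth acting on because the main claim is agreement and the remedy is inexpensive.

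**What to change.** Keep the single operator, and leave the routine clinical scan and its report unchanged.

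1. Store the MCA spectra from both machines. The documents do not say whether this was done.
2. Have the same operator re-measure TAMM from all stored spectra (about 100) in random order, under coded labels, with the paired value hidden.
3. Assign the research STOP category from these re-measured values, and use them for the ICC, the Bland-Altman analysis and the category comparison.
4. If spectra were not stored, state in the Conclusion whether the second reading was taken with knowledge of the first and, if so, that agreement may be overstated.

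The cost is an estimated few hours of the operator's time, with no extra patients, staff or procedures. The limits of agreement will probably be wider. The remedy is partial: any steering during acquisition, through the window, the choice of waveform or the gain, is already in the stored spectra and is only partly removed by coded re-measurement.

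### Complete agreement in STOP category is claimed from 25 unselected children with no category analysis planned and no counts, interval or limit to the categories observed

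*Combined protocol and SAP*

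**What the plan says.** **Sampling (Methods).** Eligibility is by age and clinic: "Patients with SCD age 2 to 16 years attending our tertiary paediatric haematology clinic for stroke surveillance were eligible". The plan then says "we aimed to study 25 consecutive patients referred to the vascular sciences department for routine TCD scanning". That number comes from service volume and a time limit: "The study was conducted as part of a higher degree in vascular imaging and hence the study duration was limited to six months". There is no velocity criterion, quota or stratum by risk category, and no precision target.

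**Category outcome (Methods).** "Each study was categorised as normal, conditional, abnormal or inadequate according to criteria previously developed by the STOP protocol". The velocity cut-points are not printed. On the portable machine, "The measurement was then repeated in every patient in only the MCA on each side of the head", so each child contributes up to two vessels.

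**Analysis (Statistical Analysis).** Spearman correlation, the ICC with a 95% interval and a benchmark of 0.75, and Bland-Altman plots for TAMM velocity. Nothing is specified for agreement in category: no table, statistic or interval.

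**Claim (Conclusion).** "This study demonstrated complete agreement in stroke risk categorisation between the two instruments". The section calls the study a pilot and adds (the quote stops in mid-sentence): "A larger sample size with a greater range in TAMM velocities is needed to further investigate the correlation between different ultrasound machines at extremes of".

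**The concern.** The portable machine would be used to place children in a STOP category, so the question that matters for screening is whether it moves a child across a cut-point. Two machines can differ in velocity and still give the same category to any child well away from a cut-point. Agreement in category is therefore informative mainly through children near or above the cut-points, and the sampling does not control how many of those there are.

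The Conclusion makes a statement about categorisation in general. A reader cannot tell from it how many children were conditional or abnormal, or whether any were. Nor does the plan contain an analysis that would show this. The risk is that the sentence is read as evidence that the portable machine classifies higher-risk children correctly, when the data behind it may include only a handful of them.

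**Working it through.** **The plan's own figure.** The target of 25 cannot be reproduced by a formula, because no effect size, category prevalence or precision target is given. It is taken as stated. The achieved number is not reported, so 25 is used below.

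**Step 1: all 25 children agree.** When n of n agree, the exact (Clopper-Pearson) two-sided 95% lower limit is 0.025^(1/n).
- n = 25: 0.025^(1/25) = 0.863. Discordance of up to 1 − 0.863 = 13.7% is compatible with complete agreement.
- If each MCA were counted separately (up to 50), the limit would be 0.025^(1/50) = 0.929. That is too optimistic, because the two sides of one child are not independent. The child is the proper unit.

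**Step 2: how many non-normal children to expect.** The documents give no category mix, so the share p is assumed and varied. The number among 25 is Binomial(25, p).

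| Assumed p | Expected, 25 × p | P(none) | P(2 or fewer) |
|---|---|---|---|
| 5% | 1.25 | 28% | 87% |
| 10% | 2.5 | 7% | 54% |
| 20% | 5.0 | 0.4% | 10% |
| 30% | 7.5 | <0.1% | 1% |

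Even at 30%, the chance of 10 or more is only 19%.

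**Step 3: what perfect agreement in those children shows.** With 0 of k discordant, the two-sided 95% upper limit for discordance is 1 − 0.025^(1/k).

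| k | Upper limit |
|---|---|
| 2 | 84% |
| 3 | 71% |
| 5 | 52% |
| 10 | 31% |

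**Step 4: could a real problem be missed?** Suppose a share f of children lie near a cut-point, each of these is discordant with probability q, and all others always agree. Then P(25 of 25 agree) = (1 − f × q)^25. Both f and q are assumptions.
- f = 10%, q = 20%: 0.98^25 = 60%.
- f = 20%, q = 20%: 0.96^25 = 36%.

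So complete agreement is a quite likely result even when one in five children near a cut-point would be classed differently.

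**The case against.** **The Conclusion is already modest.** It reports in the past tense what was observed, labels the study a pilot, asks for more children over a wider spread of velocities, and closes by saying that more evidence is needed on what the differences mean for screening. This stands in part, and the authors deserve credit for it. But the range caveat concerns correlation at very high or very low velocities. It does not limit the sentence on categorisation, and none of these statements supplies counts.

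**Category is not the planned comparison.** The planned statistics address velocity, and differences between machines in normal children do inform the size of machine error. That is right for the velocity analysis, which this point leaves untouched. It does not help the category claim, which has no analysis behind it.

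**Stronger readings that the documents do not support:**
- A reader might infer that the sample did contain few children near or above the cut-points. This is not shown. No counts, velocity distribution or cut-points are given, and high-normal children are near a cut-point too. Counts may have been reported elsewhere.
- A reader might infer that complete agreement is worthless, or arises by chance in a mostly normal sample. It does not. If 10% were non-normal and the two machines' categories were unrelated, each child would agree with probability 0.9² + 0.1² = 0.82, and all 25 with probability 0.82^25, about 0.7%. The result carries some evidence, but little about the non-normal group.
- A reader might infer that places within the 25 should have been reserved for higher-risk children. The documents show no caseload that would allow it. At an assumed 10% to 30% non-normal, filling ten such places would take on average 10/0.10 = 100 to 10/0.30 = 33 attendances, in a project limited to six months.
- A reader might infer that asking for a larger sample is mistaken because consecutive sampling keeps the same mix. The mix stays, but the counts grow: at 10%, 100 children give 10 non-normal instead of 2.5.

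**Conclusion.** The point holds as one of analysis and reporting. The documents directly support three facts: children were taken consecutively without regard to risk category, no category-agreement analysis is planned, and complete agreement in category is stated without counts, an interval or a limit to the categories observed.

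What can be said without any assumption about mix is that 25 of 25 agreeing would exclude overall discordance above about 14%, and no less. What can be said about conditional and abnormal children depends on how many there were. Over an assumed non-normal share of 10% to 30%, the data would be thin, and discordance of half or more in that group could often not be excluded. These subgroup figures illustrate the problem; they do not describe this sample. The documents do not show that the portable machine misclassifies anyone, nor that consecutive sampling was the wrong choice for a six-month pilot.

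**What to change.** 1. **Statistical Analysis.** Add a cross-table of STOP category by machine, with the child as the unit, keeping inadequate studies as their own row and column. State how the two sides are combined into one category per child. Give the proportion in agreement with exact 95% intervals, overall and separately for children who are normal and non-normal on the laboratory machine.
2. **Conclusion.** Replace the sentence on categorisation with: *agreement in category was observed in the categories represented (n normal, n conditional, n abnormal); agreement in categories with few or no children was not tested.*
3. **Follow-on work.** Keep the call for more children and a wider velocity range, and add that the next sample should be selected to cover the conditional and abnormal range.

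**Cost.** One paragraph in the analysis section, one small table and one reworded sentence, with no new children or scans. The downside is a less favourable headline and wide intervals in the non-normal group, which reflect what the sample can show.

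### The plan infers the portable scanner's validity from strength of association and an ICC above 0.75, neither of which shows that TAMM velocities agree closely enough for STOP categories

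*Combined protocol and SAP*

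**What the plan says.** The Statistical Analysis section of the combined protocol and SAP names three analyses.

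- Spearman coefficients are calculated, in "order to assess the strength of the association between the two measures".
- The ICC, with a 95% confidence interval, is described as "a measure of the strength of the association between the measurements from both pieces of equipment and therefore the validity of the measurement". The next sentence reads "It has been stated that $ICC > 0.75$ implies acceptable validity". The form of the ICC (consistency or absolute agreement) is not given, nor is it said whether 0.75 applies to the estimate or to its lower confidence limit.
- On agreement: "BlandAltman plots were used to estimate the agreement between TAMM velocity measurements by determining how much the velocity from one machine differs from another". No acceptable bias or limits are stated.

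The only other number used as a standard is the 5% significance level, which is not a criterion for agreement.

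The Methods explain that TAMM was chosen because "stroke risk categorisation according to the STOP trial was based on TAMM velocity, not peak systolic or end diastolic velocities", and they assign every study a STOP category. The portable scan was done "in only the MCA on each side of the head", so each child can contribute two pairs of readings. The Conclusion states: "This study demonstrated complete agreement in stroke risk categorisation between the two instruments". It gives no denominator or interval, and the Statistical Analysis section describes no analysis of category agreement.

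**The concern.** Association is not agreement. Two machines can rank children identically while one reads consistently lower. They can also have a high ICC while individual readings differ by tens of cm/s. A STOP category is assigned from the absolute velocity, so both kinds of error can move a child across a boundary.

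Three features of the ICC make it unsuitable as the test of validity here.

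- A value of 0.75 is compatible with wide differences even when there is no bias.
- It depends on how much the children differ, so case mix can decide whether the same machine passes.
- A consistency ICC ignores a constant offset, and an absolute-agreement ICC penalises it only in part.

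The study exists to evaluate a portable machine for stroke-risk screening. By the cited standard, that machine could be called acceptable with an offset, or with scatter large enough to change categories. The two analyses that do answer the question have no criterion and no stated precision.

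**Working it through.** The plan has no figure to reproduce: 0.75 is a cited rule of thumb, and the target of 25 children comes from patient numbers in the service over six months. The check therefore asks what an ICC of 0.75 would permit.

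**Inputs.** From the documents: ICC 0.75; a target of 25 children; two MCAs per child. Assumed: S, the total SD of one TAMM reading, of 20, 25 or 30 cm/s; normal errors; equal variances on the two machines.

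**1. Scatter without bias.** SD of differences = S × √(2 × (1 − ICC)) = 0.707 S at ICC 0.75. The 95% limits are ±1.96 × 0.707 S = ±1.39 S.

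| S (cm/s) | SD of differences | 95% limits | Pairs differing by more than 10 cm/s |
|---|---|---|---|
| 20 | 14.1 | ±27.7 | 48% |
| 25 | 17.7 | ±34.6 | 57% |
| 30 | 21.2 | ±41.6 | 64% |

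The last column is 2 × (1 − Φ(10 / SD of differences)). The 10 cm/s is only a yardstick, not a STOP quantity.

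**2. Case mix.** Fix the SD of differences at 15 cm/s. ICC = 1 − (15²/2)/S² = 1 − 112.5/400 = 0.72 at S = 20, and 1 − 112.5/900 = 0.875 at S = 30. If 20 and 30 are read as between-child SDs instead, the values are 400/512.5 = 0.78 and 900/1012.5 = 0.89. Both then pass, but the dependence on spread remains.

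**3. Offset.** Suppose the portable machine reads 0.5 S low and is otherwise identical. Spearman and the consistency ICC are both 1.00, and the absolute-agreement ICC is 1/(1 + 0.5²/2) = 0.89. At 0.75 S it is still 1/(1 + 0.75²/2) = 0.78. More realistically, with a consistency ICC of 0.90 and an offset d, the absolute-agreement ICC = 0.9 S²/(S² + d²/2). Setting this to 0.75 gives d = S√0.4 = 12.6, 15.8 and 19.0 cm/s for S = 20, 25 and 30.

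**4. Crossing a cut-off.** The documents do not give the STOP cut-offs, so a single cut-off was placed 1, 1.5 or 2 SD above the mean in a bivariate-normal simulation. This needs no SD in cm/s. At ICC 0.75, 43%, 53% and 63% of readings above the cut-off on the reference machine fall below it on the portable one. Overall discordance is 13.7%, 7.1% and 2.9%. At ICC 0.90 the first three shares are still 27%, 34% and 41%.

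**5. Precision.** MCAs within a child are not independent, so the information lies between 25 and 50 independent pairs if 25 children were scanned on both sides.

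- *ICC of 0.75, F method:* F = (1 + 0.75)/(1 − 0.75) = 7. Dividing and multiplying by the 97.5% point of F on (n − 1, n − 1) degrees of freedom, and converting back by (F − 1)/(F + 1), gives 0.51 to 0.88 for n = 25 and 0.60 to 0.85 for n = 50.
- *Each limit of agreement:* half-width of its 95% interval = t × √(1/n + 1.96²/(2(n − 1))) SDs of differences, which is 0.715 for n = 25 and 0.489 for n = 50. With an SD of 15 cm/s this is ±10.7 and ±7.3 cm/s.
- *Complete category agreement:* exact lower 95% limit = 0.025^(1/n), which is 86.3% for 25 of 25 and 92.9% for 50 of 50 (the latter only if MCAs were independent).

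**The case against.** The best defence is that 0.75 is reported as a benchmark others have used, not adopted as a decision rule, and that the Conclusion never relies on it. The Conclusion cites category agreement, calls the study a pilot, and asks for more children and a wider spread of velocities. Bland-Altman plots are planned, and estimating limits without a margin is defensible in a pilot sized by clinic throughput. The sizes above rest on assumed SDs, an ICC of exactly 0.75 and assumed cut-off positions. The text is in the past tense with a conclusion attached, so nothing can now be prespecified.

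Much of this is fair. The figures show what the benchmark would permit, not what this study found, and the observed ICC may have been higher. The number of children behind the complete agreement is not stated, so 25 of 25 is conditional. A tolerance set now would be post hoc.

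None of it rescues the inference. The benchmark directly follows the step from association to validity, and no other standard is offered. Pilot status excuses the sample size, not the logic. The Conclusion's appeal to category agreement exposes the gap further, because the analysis section does not describe that analysis. The wish for a wider velocity range concedes that agreement at the extremes is unsettled.

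**Conclusion.** The concern holds and the change is needed, because the fault lies in the central inference of the study. Neither strength of association nor an ICC above 0.75 establishes that the portable machine's TAMM velocities can stand in for the reference machine's when STOP categories are assigned. The sizes in cm/s depend on the assumed SD of 20 to 30 cm/s for one reading. The offset result also assumes a consistency ICC of 0.90, and the cut-off result assumes normality and a single boundary. Three conclusions do not depend on any particular SD: limits of ±1.39 SD at ICC 0.75 without bias, the dependence of the ICC on case mix, and its incomplete response to an offset.

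**What to change.** 1. In the Statistical Analysis section, delete the clause that derives validity from association, and delete the sentence saying that an ICC above 0.75 "implies acceptable validity".
2. Base validity on the Bland-Altman mean difference and 95% limits of agreement. Give each a 95% confidence interval that allows for two MCAs per child, with child as a random effect or a bootstrap by child. Judge them by whether a reading near a STOP cut-off could change category. State the tolerated difference in cm/s and how it follows from the cut-offs, and label it post hoc if it is set after the data were seen. No figure is proposed here because the documents do not give the cut-offs.
3. Examine the difference against the mean, so that the limits are not assumed constant up to high velocities.
4. Add between-machine STOP category agreement per child: a cross-table with its denominator and an exact 95% confidence interval. Use MCA readings from both machines, since the portable scan covers only the MCA.
5. Keep the ICC as supportive, in absolute-agreement, single-measure form with its interval and no pass mark. Keep Spearman as descriptive.

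The cost is rewording and some further analysis of data already collected, with no extra scans. The downside is a weaker claim: complete agreement in 25 children, if that was the number, would still leave disagreement of up to about 14% (100% − 86.3%) inside the 95% interval.
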